5.4 Treatment Assignment and Duration

Patients with unilateral BCRL will be randomized (1:1) to receive one of the following treatments in the affected limb:

- Approximately 60 minutes of treatment with Flexitouch Plus (FT); or
- Approximately 40 minutes of treatment with Flexitouch Plus with Novel Simultaneous Therapy Cycle Software (FT-SW)

5.5 Study Timeline

The expected study duration is approximately 8 months with 2-3 months spent on activation, 3 months enrolling subjects, and 2 months completing the data analysis.

6.0 Study Assessments

Case Report Forms (CRFs) and Data Clarification Forms (DCFs) will be used for data collection and query handling. The Investigator will ensure the accuracy, completeness, and timeliness of the data recorded and responses to data queries according to the Clinical Trial Agreement (CTA). NIRF data collected and recorded by the Investigator, and perometry data collected and recorded by LymphaTech, will be obtained and reconciled against study data.

All data entry, storage, transmission, and management will be conducted using iMedNet, a 21 CFR Part 11 compliant electronic data capture (EDC) system. When all data have been validated, signed, and locked, the database will be locked and available for analysis.

All devices and testing procedures outlined are standard of care or approved/cleared for use by the FDA with the exception of FT-SW and NIRF imaging (which is approved by the FDA for investigational use in humans under an existing IND #102,765). Prior to taking endpoint measurements, delegated personnel will receive training and will demonstrate proficiency.

6.1 Screening/Baseline

If a patient appears eligible to participate based on medical history, he or she will be approached to participate in the study and consented if interested in participating. All consented subjects will undergo the following procedures:

- Obtain medical history
- Administer a serum or urine pregnancy test for all female subjects of child-bearing potential (for imaging purposes, the pregnancy test should be done \leq 36 hours prior to NIRF imaging)
- Vital signs – historic values within past 7 days may be used
- Subject survey – Edmonton Symptom Assessment System (ESAS-R)
- Lymphedema evaluation
- Perometry via LymphaTech 3D scanner to determine volume of affected and unaffected arm
 - If the subject's volume difference is $<5\%$ between affected and unaffected arm, they will be considered a screen failure and will not continue in the study
- Mark Anatomical Sites
- ICG Injections
- The following assessments will be performed on the affected and unaffected arm in the order listed
 - MoistureMeterD (MMD) to assess local tissue water (LTW) content
 - Ultrasound to assess skin thickness
 - NIRF imaging to assess lymphatic activation
- Randomization

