Inclusion/Exclusion	
Inclusion Criteria:
 
 Female 18 years of age or older Diagnosis of unilateral breast cancer-related lymphedema Stage I or early Stage II lymphedema without severe fibrosis at the time of enrollment ≥ 5% volume difference between affected and unaffected arm as verified via perometry (LymphaTech 3D scanner) Willing and able to give informed consent Willing and able to comply with the study protocol requirements and all study-related visit requirements 
Exclusion Criteria:
 
 In-home use of pneumatic compression device (PCD) within previous 3 months

	
 2. Therapist or self-administered manual lymph drainage (MLD) within previous 1 week 3. Mastectomy or lymph node removal on side without lymphedema 4. Bilateral lymphedema 5. Heart failure (acute pulmonary edema, decompensated acute heart failure) 6. Acute venous disease (acute thrombophlebitis, acute deep venous thrombosis, acute pulmonary embolism) 7. Active skin or limb infection/inflammatory disease (acute cellulitis, other uncontrolled skin or untreated inflammatory skin disease) on the arms or trunk 8. Active cancer (cancer that is currently under treatment, but not yet in remission) 9. Poorly controlled kidney disease (glomerular filtration rate < 30 mls per minute), hypoproteinemia, pulmonary hypertension, hypothyroidism, cyclic edema, or Munchausen Syndrome 10. Body Mass Index (BMI) >50 11. Any circumstance where increased lymphatic or venous return is undesirable 12. Currently pregnant or trying to become pregnant 13. Allergy to iodine
Treatment Duration	
A single treatment lasting:
 
 • FT-SW: Approximately 40 minutes OR • FT: Approximately 60 minutes
Number Planned	20 subjects randomized (minimum of 10 in each arm) with replacement of up to 5 early withdrawals.

TABLE OF CONTENTS

1.0	Contact Information	7
1.1	Sponsor Contact Information.....	7
1.2	Principal Investigator Information.....	7
1.3	Clinical Investigator Information	7
2.0	Abbreviations	8
3.0	Introduction.....	10
3.1	Background and Rationale.....	10
3.2	Device Description	10
4.0	Study Objective.....	13
5.0	Study Design.....	13
5.1	Endpoints	13
5.2	Subject Selection	14
5.3	Point of Enrollment and Randomization	15
5.4	Treatment Assignment and Duration.....	15
5.5	Study Timeline	15
6.0	Study Assessments.....	15
6.1	Screening/Baseline	16
6.2	Randomization.....	16

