5.1 Endpoints

To compare the effects of FT to FT-SW in BCRL patients after one treatment based upon:

- Lymphatic activation in the affected and contralateral limb using the investigational technique of near infrared-fluorescent (NIRF) imaging
- Swelling in the affected and contralateral limb as assessed using:
 - Perometry (LymphaTech 3D Scanner)
 - Local tissue water content (MoistureMeterD)
- Skin changes on the affected and contralateral limb as assessed by:
 - Skin thickness (Ultrasound)
- Safety

Table 1. Outcome Measures

Endpoint	Outcome Measure
Lymphatic activation	
 Proportion of subjects who show an increase in the number of functional vessels and/or area of dermal backflow per NIRF imaging of the affected and contralateral arm when comparing post-treatment values to pre-treatment values Proportion of subjects who show an increase of lymphatic propulsion events immediately after treatment
Changes in Swelling	
 Proportion of subjects who show a decrease in arm perometry (limb volume) when comparing post-treatment values to pre-treatment values for the affected and contralateral arm Proportion of subjects who show a decrease in local tissue water at target sites when comparing post-treatment values to pre-treatment values for the affected side Mean change in perometry and local tissue water post-treatment will be compared for all sites
Skin Changes	
 Proportion of subjects who show a decrease in skin thickness at target site when comparing post-treatment values to pre-treatment values for the affected side Mean change in skin thickness post-treatment will be compared for all sites
Safety	
 Adverse events will be presented in data listings

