5.2 Subject Selection

The target population includes patients who have received breast cancer therapy and developed unilateral lymphedema secondary to their cancer treatment. Patients will be recruited from the clinical investigator's patient population.

5.2.1 Inclusion Criteria:

1. Female 18 years of age or older
2. Diagnosis of unilateral breast cancer-related lymphedema
3. Stage I or early stage II lymphedema without severe fibrosis at the time of enrollment
4. $\geq 5\%$ volume difference between affected and unaffected arm as verified via perometry (LymphaTech 3D scanner)
5. Willing and able to give informed consent
6. Willing and able to comply with the study protocol requirements and all study-related visit requirements

5.2.2 Exclusion Criteria:

1. In-home use of PCD within previous 3 months
2. Therapist or self-administered manual lymph drainage (MLD) within previous 1 week
3. Mastectomy or lymph node removal on side without lymphedema
4. Bilateral lymphedema
5. Heart failure (acute pulmonary edema, decompensated acute heart failure)

6. Acute venous disease (acute thrombophlebitis, acute deep venous thrombosis, acute pulmonary embolism)
7. Active skin or limb infection/inflammatory disease (acute cellulitis, other uncontrolled skin or untreated inflammatory skin disease) on the arms or trunk
8. Active cancer (cancer that is currently under treatment, but not yet in remission)
9. Poorly controlled kidney disease (glomerular filtration rate < 30 mls per minute), hypoproteinemia, pulmonary hypertension, hypothyroidism, cyclic edema, or Munchausen Syndrome

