6.4 Post-Treatment Testing

After the subject has completed treatment, the Flexitouch garments will be removed. The following assessments will be performed on affected and unaffected arm in the order listed and should begin within approximately 15 minutes of the completion of treatment:

- Perometry via Lymphatech 3D Scanner to determine volume
- MoistureMeterD (MMD) to assess local tissue water (LTW) content
- Ultrasound to assess skin thickness
- NIRF imaging to assess lymphatic activation
- Subject surveys
 - ESAS-R
 - Treatment Perception Survey
- Adverse Event Assessment

6.5 24-Hour Follow-up

Subjects will return to the clinic or be contacted via telephone 18-28 hours after ICG injection for assessment of adverse events.

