8.5 Subject Surveys

Prior to treatment the subject will complete the ESAS-R. After treatment and assessments are completed, the subject will complete the ESAS-R and a Treatment Perception survey.

8.6 **Lymphedema Evaluation**

Research personnel will confirm the presence of Stage I or early Stage II lymphedema and severity of fibrosis at Screening/Baseline. The clinical stage of lymphedema will be evaluated by a clinician using the following definitions:

- Stage 0: Latent – No clinical signs (no evident swelling)
- Stage 1: Soft swelling (pitting) that resolves with elevation
- Stage 2: Spongy swelling (pitting and non-pitting) that does not resolve with elevation; fibrosis may or may not be present
- Stage 3: Symptoms of lymphostatic elephantiasis where pitting is absent and trophic skin changes develop; extensive fibrotic swelling, blistering, ulceration, lymphorrhea, papilloma, and/or recurrent infections may be present

Severity of fibrosis, to distinguish between early and late Stage II lymphedema, will be based on the definitions below:

Table 3. Fibrosis Assessment

None	No fibrotic tissue
Minimal	Able to move skin parallel to plane (sliding) and perpendicular to skin (pinching up), <20% of affected limb noted to have fibrotic tissue
Moderate	Able to slide skin, unable to pinch skin, 20-40% of affected limb noted to have fibrotic tissue
Severe	Unable to slide or pinch skin, >40% of affected limb noted to have fibrotic tissue

8.7 **Perometry**

Perometry will be performed on both limbs before and after treatment. The LymphaTech 3D Scanner will be utilized by appropriately trained research personnel in accordance with the instructions for use provided by LymphaTech.

8.8 **Marking Anatomical Sites**

Have the subject pull-up/remove clothing if covering arms. Using a pen or marker, with the subject in a seated or standing position with arms completely relaxed at sides, mark the skin at the locations outlined in Figures 3-5 on affected and unaffected sides.

If a subject experiences pain at a targeted measurement site, an alternate location may be measured, recorded, and used for the duration of the study.

[figure not shown]

Figure 3. Site A is on the anterior forearm 6 cm below (distal to) the midline of the antecubital fossa.

Figure 4. Site B is 6 cm above (proximal to) the dorsal aspect of the wrist (midline).

Figure 5. Site C is 3 cm distal to the midline dorsal aspect of the wrist.

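### One perometry scan both admits the subject and supplies her pre-treatment volume, so within-arm volume changes carry regression to the mean; the FT-SW versus FT difference does not

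*Combined protocol and SAP*

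**What the plan says.** Inclusion criterion 4 (section 5.2.1) requires an inter-arm volume difference of at least 5%, verified on the study scanner. Section 6.1 lists this step among the screening/baseline procedures as "Perometry via LymphaTech 3D scanner to determine volume of affected and unaffected arm", and says of subjects below the threshold "between affected and unaffected arm, they will be considered a screen failure and will not continue in the study". The baseline assessments that follow are tissue water, ultrasound and NIRF, with no further perometry. Table 2 likewise shows a single perometry entry before treatment, under Screening.

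Section 8.7 states "Perometry will be performed on both limbs before and after treatment". Section 6.4 places "Perometry via Lymphatech 3D Scanner to determine volume" first among the post-treatment assessments. Table 1 (section 5.1) then uses the two scans in two outcomes: "Proportion of subjects who show a decrease in arm perometry (limb volume) when comparing post-treatment values to pre-treatment values", for each arm of the body, and "Mean change in perometry and local tissue water post-treatment will be compared for all sites". The proportion counts any decrease, with no minimum size.

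Randomization comes after all baseline assessments (section 6.2), to two active treatments. The planned size is "20 subjects randomized (minimum of 10 in each arm) with replacement of up to 5 early withdrawals". Section 16 plans estimation without formal tests. It mentions no baseline adjustment and does not say how mean changes will be compared. Neither replicate scans nor a scanner repeatability figure is given.

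**The concern.** A subject near 5% is more likely to be kept when scan error makes her affected arm read high or her unaffected arm read low. The post-treatment scan has undergone no such selection. On average, therefore, the affected arm appears to shrink and the contralateral arm to grow even if nothing has changed.

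Both groups receive an active device, and no untreated or sham group would expose the artefact. The trial's direct evidence that either device reduces volume is the within-arm change, and that is the quantity affected. A similar decrease under both devices could be taken as two devices working equally well, when part of it comes from the entry rule. Section 17 says the data are meant to support product development and marketing claims, so a within-arm figure may well be used on its own.

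**Working it through.** The plan gives no figure to reproduce, because it states no scanner error and no expected distribution of arm differences. Both are assumed below and varied.

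**Inputs from the protocol.** Entry threshold 5% (5.2.1, 6.1); one scan before and one after treatment (6.1, 6.4, 8.7); outcomes are any decrease and mean change (Table 1); 10 per group (synopsis).

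**Assumptions.** All quantities are in % of unaffected-arm volume. True difference D ~ N(μ, τ), where τ is an SD. Scan errors are independent for each limb and each scan, with SD σ. There is no true change between scans.

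**Formula.** The measured difference is M = D + e_A − e_U, with SD s = √(τ² + 2σ²). A subject is admitted if M ≥ 5. With a = (5 − μ)/s and λ = φ(a)/(1 − Φ(a)):

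- expected affected-arm change = −(σ²/s)·λ
- expected contralateral change = +(σ²/s)·λ

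**Worked cases.**

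- μ = 5, τ = 4, σ = 2: s = √(16 + 8) = 4.899; a = 0; λ = 0.798; shift = −(4/4.899) × 0.798 = −0.65.
- μ = 8, τ = 5, σ = 2: s = √(25 + 8) = 5.745; a = −0.522; λ = 0.498; shift = −(4/5.745) × 0.498 = −0.35.

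**Results with no treatment effect** (mean change from the formula and confirmed by simulation; share with a decrease by simulation):

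| True difference (μ, τ) | σ | Affected-arm mean change | Share with affected-arm decrease |
|---|---|---|---|
| 5, 4 | 1 / 2 / 3 | −0.19 / −0.65 / −1.23 | 55% / 59% / 62% |
| 8, 5 | 1 / 2 / 3 | −0.09 / −0.35 / −0.73 | 53% / 55% / 57% |
| 12, 8 | 1 / 2 / 3 | −0.04 / −0.17 / −0.38 | 51% / 52% / 54% |

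The contralateral arm moves by the same amount in the opposite direction. In the first row, 45%, 41% and 38% of subjects show a decrease there.

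**When it is small.** With σ = 0.5 the mean shift in these three scenarios is −0.01 to −0.05 and the share 51-53%. With true differences spread evenly from 10% to 30% and σ = 1 or 2, the shift is at most 0.01 and the share 50%.

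**Between devices.** In simulated trials of 10 per group (μ = 8, τ = 6, σ = 2) the within-group mean change is −0.32, while the average difference between groups is 0.00.

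**A separate baseline scan.** When a second, unselected scan serves as baseline, the null mean change is 0.00 and the share 50% in all five scenarios run. For comparison, reusing the entry scan gives −0.32 and 54.6% (μ = 8, τ = 6, σ = 2), and −0.76 and 61.0% (μ = 5, τ = 3, σ = 2).

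**Consequence with 10 subjects.** The probability of at least 7 decreases is 17% if the true share is 50%, 27% at 55% and 38% at 60%.

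**The case against.** The strongest reply is that the trial's stated purpose is to compare the two devices, and that comparison is sound. This stands. A reader might infer that the entry rule biases the equivalency comparison, but subjects are randomized after the scan, so selection acts equally on both groups in expectation.

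Secondly, materiality is not shown. The top of the range needs a 3% scan error per limb and a population mean exactly at the threshold. That would imply that half of those scanned fail screening and that about 11% have a truly smaller affected arm (Φ(−5/4) = 0.106), in women already diagnosed and clinically evaluated. This also stands: the effect may be negligible. It is tempting to argue that the criteria select mild disease close to 5%. They do not establish that. Section 8.6 stages by pitting, response to elevation and fibrosis, not by volume, and the 5% rule has no upper limit.

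Thirdly, sampling noise is larger. With 10 subjects the standard error of a proportion near 50% is √(0.25/10) = 16 points. In the between-device simulation above, the SD of change is 2.79, so the standard error of a mean is 2.79/√10 = 0.88 against a shift of −0.32. That is so, but noise widens an interval, whereas this shift moves its centre in a known direction and can be avoided. It is also true that scan error alone gives about 50% decreases without any selection. That is a separate and probably larger weakness of counting any decrease.

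Fourthly, an affected-minus-contralateral contrast would double the shift (−0.65 − 0.65 = −1.30 in the first worked case). Table 1 defines no such contrast, so the doubled figure does not describe a planned outcome. Table 1 does report the contralateral arm, where the mirror-image rise is a partial warning sign.

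Finally, the scan precedes the injections and the other baseline measurements, and one might suspect that limb changes in that interval pass for treatment effect. The documents give neither a size nor a direction for this, and injected fluid would work against an apparent decrease. It adds a reason for a later scan but is not counted here.

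**Conclusion.** The point holds for the within-arm volume outcomes only. Following the plan as written shifts the affected arm towards a decrease and the contralateral arm towards an increase under both devices, and nothing in section 16 removes this. The expected FT-SW minus FT difference is unaffected.

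The direction is certain given any scan error. The size rests on assumed error and assumed arm differences: for σ of 1-3%, from −0.04% to −1.2% of arm volume and a 51-62% share with a decrease, and close to nil in mean change if the scanner is precise or subjects lie well above 5%. The documents do not support calling it large, nor calling the device comparison biased. Priority: low to moderate.

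**What to change.** In section 16, base the volume comparison on the FT-SW minus FT difference in post-treatment volume, adjusted for the pre-treatment volume already collected, and report it with a confidence interval. State there that within-arm volume decreases are not evidence of treatment effect and are to be read beside the contralateral arm, not after subtracting it, since subtraction doubles the shift. This costs only wording.

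Preferably also repeat the scan of both arms just before treatment. Keep the first scan for the 5% check alone, and define the second as the pre-treatment value in section 8.7 and Table 1. The scan is non-invasive and the device is already provided to the site (section 10). The cost is a slightly longer visit and possibly a less favourable within-arm figure.

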6.2 Randomization

Randomization will occur after all of the screening/baseline assessments are complete. The study personnel performing study assessments will remain blinded to the treatment assignment.

6.3 Treatment

The randomized treatment assignment will be administered to the affected limb. The personnel administering the treatment will not perform any study assessments as they will be unblinded to the treatment.

6.4 Post-Treatment Testing

After the subject has completed treatment, the Flexitouch garments will be removed. The following assessments will be performed on affected and unaffected arm in the order listed and should begin within approximately 15 minutes of the completion of treatment:

- Perometry via Lymphatech 3D Scanner to determine volume
- MoistureMeterD (MMD) to assess local tissue water (LTW) content
- Ultrasound to assess skin thickness
- NIRF imaging to assess lymphatic activation
- Subject surveys
 - ESAS-R
 - Treatment Perception Survey
- Adverse Event Assessment

6.5 24-Hour Follow-up

Subjects will return to the clinic or be contacted via telephone 18-28 hours after ICG injection for assessment of adverse events.

7.0 Study Schedule of Activities

The study schedule of activities is shown below (Table 2).

Table 2. Schedule of Activities

Procedures	Day 0 (Acute Study)			24 hour follow-up
	Screening	Treatment	Post-Treatment	
Informed Consent	X			
Demographics & Medical History	X			
Inclusion/Exclusion Assessment	X			
Pregnancy Test (if applicable)	X			
Vital Signs	X			
Subject Surveys	X			X
Lymphedema Evaluation	X			
Perometry (LymphaTech 3D Scanner)	X			X
Mark Anatomical Sites	X			
ICG Injection	X			
LTW (MoistureMeterD)	X			X
Ultrasound	X			X
NIRF Imaging	X			X
Randomization	X			
FT or FT-SW Treatment			X	
Adverse Event Assessment	X	X	X	X

8.0 Study Procedures

8.1 Informed Consent

Subjects will need to sign an informed consent form that has been approved by both the Sponsor and reviewing IRB to be considered for participation in this study. Subjects must meet all of the inclusion and none of the exclusion criteria.

Each subject (or a legally authorized representative) must give written consent, in accordance with local requirements, after the nature of the study has been fully explained and questions answered. The consent form must be signed prior to any study-related procedures, and the process of informed consent must be documented in the subject's record.

8.2 Demographics & Medical History

Demographics will be collected including the age at time of participation, ethnicity, race, and sex.

Significant medical history, including lymphedema history, will be collected.

8.3 Pregnancy Test

Women of childbearing potential will be tested for pregnancy according to the site specific procedures at the Screening/Baseline visit. If the pregnancy test is positive, the subject will not be enrolled in the study.

8.4 Vital Signs

Height and weight will be collected to confirm subject's BMI is <50.

8.5 Subject Surveys

Prior to treatment the subject will complete the ESAS-R. After treatment and assessments are completed, the subject will complete the ESAS-R and a Treatment Perception survey.

8.6 **Lymphedema Evaluation**

Research personnel will confirm the presence of Stage I or early Stage II lymphedema and severity of fibrosis at Screening/Baseline. The clinical stage of lymphedema will be evaluated by a clinician using the following definitions:

- Stage 0: Latent – No clinical signs (no evident swelling)
- Stage 1: Soft swelling (pitting) that resolves with elevation
- Stage 2: Spongy swelling (pitting and non-pitting) that does not resolve with elevation; fibrosis may or may not be present
- Stage 3: Symptoms of lymphostatic elephantiasis where pitting is absent and trophic skin changes develop; extensive fibrotic swelling, blistering, ulceration, lymphorrhea, papilloma, and/or recurrent infections may be present

Severity of fibrosis, to distinguish between early and late Stage II lymphedema, will be based on the definitions below:

Table 3. Fibrosis Assessment

None	No fibrotic tissue
Minimal	Able to move skin parallel to plane (sliding) and perpendicular to skin (pinching up), <20% of affected limb noted to have fibrotic tissue
Moderate	Able to slide skin, unable to pinch skin, 20-40% of affected limb noted to have fibrotic tissue
Severe	Unable to slide or pinch skin, >40% of affected limb noted to have fibrotic tissue

8.7 **Perometry**

Perometry will be performed on both limbs before and after treatment. The LymphaTech 3D Scanner will be utilized by appropriately trained research personnel in accordance with the instructions for use provided by LymphaTech.

8.8 **Marking Anatomical Sites**

Have the subject pull-up/remove clothing if covering arms. Using a pen or marker, with the subject in a seated or standing position with arms completely relaxed at sides, mark the skin at the locations outlined in Figures 3-5 on affected and unaffected sides.

If a subject experiences pain at a targeted measurement site, an alternate location may be measured, recorded, and used for the duration of the study.

[figure not shown]

Figure 3. Site A is on the anterior forearm 6 cm below (distal to) the midline of the antecubital fossa.

Figure 4. Site B is 6 cm above (proximal to) the dorsal aspect of the wrist (midline).

Figure 5. Site C is 3 cm distal to the midline dorsal aspect of the wrist.

